All data needed for this study including blood loss, need for transfusion, preoperative and lowest postoperative hematocrit and hemoglobin, and complications will be collected during the hospitalization. Subject's study participation will end at hospital discharge. Costs of each component of the hospital stay will also be obtained and recorded. Adverse events will be recorded on case report form and submitted to the Duke IRB per Adverse Event policy.

The recruitment goal of this study is to enroll 75% of eligible subjects electing to undergo either primary hip or knee arthroplasty performed by three attending surgeons at this institution over a year time period.

5. Selection of Subjects

Adult patients aged 18 and over electing to undergo primary total hip or knee arthroplasty will be considered for inclusion in the proposed study and identified preoperatively.

6. Subject Identification, recruitment, and compensation

Adult patients aged 18 and over electing to undergo primary total hip or knee arthroplasty will be considered for inclusion in the proposed study and identified preoperatively. Exclusion criteria will include history of stents, MI, CVA, DVT, PE,

color blindness, and hypercoagulable state. Females of childbearing age will also have a serum pregnancy test drawn before inclusion in this study. A positive pregnancy will result in exclusion from the study. We aim to recruit 400 subjects, 200 total hip and 200 total knees. Subjects may withdraw at anytime. Post operatively, surgery data will be collected via the electronic medical record. Consent will be signed and witnessed before surgery takes place in clinic.

7. Consent Process

The investigator or his/her authorized designee will inform the subject of all aspects pertaining to the subject's participation in the study during the consent process. The process of obtaining informed consent will be in accordance with all applicable regulatory requirements (Federal Register Vol. 48, No. 17, 1982, pp 8951-2).

8. Subject's Capacity to Give Legally Effective Consent

Each patient aged 18 years or older will consent for him or herself. If the patient is less than 18 years of age they will not be considered for the study.

9. Study Interventions

Subjects will be randomly assigned in a 1:1 ratio to either an Amicar or TXA arm which are both standard of care at Duke. Subject's study participation will end at hospital discharge.

10. Risk/Benefit Assessment

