Subject or *their* insurance provider will be responsible for all costs related to your medical care, including the drugs used in this study.

No direct monetary compensation will be offered for inclusion in the proposed study.

12. Data Analysis & Statistical Considerations

Subject characteristics and study results including those outlined above (considered complications or adverse events) will be recorded. ¹ The primary endpoint for this study is the percentage of patients requiring transfusions. The secondary endpoint include total blood loss (recorded as estimated blood loss intraoperatively as determined by anesthesia staff, and postoperatively recorded by nurses from the output in drains), change in hemoglobin (preoperative vs. postoperative hemoglobin that is routinely measured before discharge), and the total cost of hospitalization as billed by Duke University (including pharmacy cost, price each night in hospitalization, all other charges incurred during admission). Binary variable results will be compared using chi-square and Fisher's exact tests (where appropriate). We plan a comparison of continuous variable results using Wilcoxon rank sum and t-tests (where appropriate). We will consider multivariable logistic regression in determination of TXA and Amicar and their correlation with the above listed complications and adverse events. Anesthetic techniques will be recorded for analysis and covariate analysis will be performed at the end of the study. In order to perform a cost analysis, total cost of hospitalization including pharmacy cost, potential transfusion costs, and cost of stay. Based on the one small European study, sample size for finding the difference between two proportions was calculated using a proportion of 0.125 patients given Amicar were transfused (n=32 vs. 0.028 (n=35) given TXA. Using an alpha value of .05 and power of .90 it was determined that there would need to be 154 patients in each sample size to find a significant difference in independent samples. Our goal of enrolling 400 patients total (200 in each arm) will therefore be appropriate for this study

13. Data & Safety Monitoring

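### The main analysis of hemoglobin change is not adjusted for preoperative hemoglobin, and the postoperative value is defined in two ways; pre-specifying ANCOVA on one definition would usually gain precision at almost no cost

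*Combined protocol and SAP*

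**What the plan says.** Section 12 lists among the secondary endpoints "change in hemoglobin (preoperative vs. postoperative hemoglobin that is routinely measured before discharge". All continuous outcomes share one sentence of method: "We plan a comparison of continuous variable results using Wilcoxon rank sum and t-tests (where appropriate". Nothing says what makes either test appropriate.

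Two other sentences in Section 12 concern adjustment. One reads "We will consider multivariable logistic regression in determination of TXA and Amicar and their correlation with the above listed complications and adverse events"; it is a logistic model for complications and adverse events and does not reach hemoglobin. The other reads "Anesthetic techniques will be recorded for analysis and covariate analysis will be performed at the end of the study"; it gives no model, endpoint or covariate list, and anesthetic technique is the only variable named.

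The data list in Section 4 (Study Design) describes the measurement differently from Section 12: "preoperative and lowest postoperative hematocrit and hemoglobin".

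Hemoglobin is not the primary endpoint: "The primary endpoint for this study is the percentage of patients requiring transfusions".

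**The concern.** There are two separate issues, and solving one does not solve the other.

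**Precision.** Preoperative hemoglobin is recorded and should correlate with the postoperative value. Subtracting it forces its coefficient to be exactly 1. If the true slope of post on pre is different, the comparison carries avoidable noise, and part of any chance baseline difference between arms stays in the estimate. Since the covariate analysis is unspecified, the plan also does not say whether an adjusted or an unadjusted result is the main one.

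**Definition.** The lowest value and the pre-discharge value can be different measurements, so either could be analyzed under the present text. A value drawn after transfusion has been raised by the event that forms the primary endpoint. The trial's hypothesis is that fewer TXA patients are transfused. If the Amicar arm bleeds more and is transfused more, its pre-discharge hemoglobin is restored more often and the difference between arms shrinks.

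**Working it through.** **The plan's own figure.** Section 12 gives no calculation for hemoglobin, only 154 per arm for transfusion (0.125 vs 0.028; "Using an alpha value of .05 and power of .90"). Sidedness is not stated. The two-sided normal formula with pooled variance under the null is

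n = [1.960·√(2 × 0.0765 × 0.9235) + 1.2816·√(0.125 × 0.875 + 0.028 × 0.972)]² / 0.097² = 155.7, so 156.

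The unpooled version gives 153. The stated 154 is therefore reproduced closely. Power is 89.7% at 154 per arm and 95.7% at the planned 200 per arm. None of this depends on the hemoglobin analysis.

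**Inputs for hemoglobin.** From the documents: 200 per arm (Section 12) and 1:1 allocation (Section 9). Not in the documents, so assumed: the pre-post correlation r, taken from 0.3 to 0.9, and the SD ratio k = SD(post)/SD(pre), first set to 1. The 80% starting power is a reference point only, because the plan sets no power target for hemoglobin.

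**Variances**, in units of the preoperative variance:

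- change score: 1 + k² − 2rk
- ANCOVA: k²(1 − r²)
- difference: (1 − rk)², which is never negative and is zero only when the slope rk equals 1.

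At k = 1 the ratio of ANCOVA to change score is (1 − r²)/[2(1 − r)] = (1 + r)/2.

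**Power.** If the change-score test has 80% power, the effect is 1.960 + 0.842 = 2.802 standard errors. ANCOVA power is Φ(2.802/√ratio − 1.960).

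| r (k = 1) | variance ratio | per arm to match 200 on change | ANCOVA power |
|---|---|---|---|
| 0.3 | 0.65 | 130 | 93.5% |
| 0.5 | 0.75 | 150 | 89.9% |
| 0.7 | 0.85 | 170 | 86.0% |
| 0.8 | 0.90 | 180 | 84.0% |
| 0.9 | 0.95 | 190 | 82.0% |

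**Unequal SDs.** At r = 0.5 the ratio is 0.571 for k = 0.8 and 0.893 for k = 1.25. At r = 0.8 and k = 1.25 the slope is 1 and the ratio is 1.000. A simulation with 200 per arm and 4,000 replicates gave 1.002 for that case, and 0.735 for r = 0.5, k = 1 (theory 0.75).

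**Transfusion effect on a pre-discharge value.** Planned gap: 0.125 − 0.028 = 0.097. Assume that each unit raises hemoglobin by 1 g/dL, that a transfused patient receives 1 to 2 units, and that the value is drawn afterwards. The difference hidden is 0.097 × 1 = 0.10 to 0.097 × 2 = 0.19 g/dL, or about 0.1 to 0.2 g/dL.

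**The case against.** A reader might draw four stronger conclusions that the documents do not support.

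- *The preoperative value is wasted.* It is not. Subtraction uses it with a fixed coefficient, and at equal SDs with r above 0.5 the change score is already more precise than the postoperative value alone.
- *ANCOVA is strictly better.* It ties when the slope is 1, it costs a degree of freedom per covariate (trivial with 400 patients), and nothing here shows that it beats Wilcoxon for skewed data.
- *The plan has no adjusted analysis.* It promises one. The gap is that its content and its rank beside the unadjusted tests are not stated.
- *The hemoglobin comparison is biased toward no difference.* This is conditional. The documents do not give the timing of draws relative to transfusion, and a routine measurement before discharge need not be the last one. The direction also requires that the arm transfused more is the arm with the larger fall.

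It is also fair to say that the t-test on change is valid in a randomized trial, that its standard error already allows for chance baseline imbalance, and that the endpoint is secondary. The size of the gain rests on r and k, and neither is in the documents. The 0.1 to 0.2 g/dL rests on assumed units and an assumed rise per unit; without an SD it cannot be set against a detectable difference.

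The lowest value has weaknesses too. Transfusion can halt a fall before the minimum is reached, and a minimum depends on how many draws each patient has. Adjusting for joint is reasonable with 200 hips and 200 knees planned (Section 6), but no gain from it has been calculated.

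All of this limits the claim. It does not supply the missing specification or reconcile the two definitions.

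**Conclusion.** The point holds as an inexpensive improvement to a secondary analysis, together with one inconsistency that needs correcting. It is not a flaw that invalidates a result.

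On precision, ANCOVA is at least as precise as the change score in large samples under 1:1 allocation. The gain runs from 35% less variance at r = 0.3 to 5% at r = 0.9 with equal SDs, and is nil when the slope is 1.

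On definition, Sections 4 and 12 describe different postoperative values, and the plan does not say how transfusion is handled. The possible masking of about 0.1 to 0.2 g/dL applies only if the pre-discharge value follows transfusion, the planned rates hold, and the arm that bleeds more is transfused more.

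**What to change.** In Section 12, give hemoglobin its own analysis sentence. The main analysis is a linear regression of postoperative hemoglobin on arm, preoperative hemoglobin and joint (hip or knee), reporting the adjusted mean difference with a 95% CI. Wilcoxon on the change becomes a sensitivity analysis, which removes the open choice of test. State what the promised covariate analysis contains and that it ranks below this model.

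Use one definition of the postoperative value in Sections 4 and 12, preferably the lowest in-hospital value, which is already collected. Add that this reduces but does not remove the effect of transfusion, and that it depends on the number of draws.

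The cost is a few sentences, with no new data and no change to the sample size. Settling on the lowest value does redefine a secondary endpoint in Section 12, so it should be recorded as such and made before outcomes are compared by arm.
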